3.5.3 Handling of missing values/censoring/discontinuations

Patients with missing assessments that prevent the evaluation of the ORR will be considered non-responders. This includes aGvHD response assessments at baseline and Days 28, 56. Patients who discontinue the study treatment prior to the completion of the Day 28 visit will be considered non-responders.

The following analysis windows will be applied to the target day for assessments on overall response, where target day for Week X is X*7.

Baseline assessment is the last aGvHD assessment prior to or at the start of study treatment (Day 1).

Weeks 1, 2, 3, 4, 5, 6, 7, 8: -3 days/+3 days

Weeks 12 to 48: -13 days/+14 days

3.5.4 Supportive analyses

The subgroup analyses to assess the homogeneity of the treatment effect across demographic and baseline disease characteristics will be performed on the EES as appropriate. The subgroups are described in section 2.2.1.

A sensitivity analysis excluding subjects who had protocol deviations of organ staging or aGvHD response assessments not strictly following standard criteria defined in study protocol (PDID: OTHER03, OTHER04 per ECS) at Day 28 will be conducted.

Efficacy analyses in subgroups will be purely exploratory and are intended to explore the consistency of treatment effect. No inferential statistics (p-values) will be produced for the subgroups.

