The content of SAP amendment 1 was based on protocol CINC424F12201, versions 1 and 2. SAP Amendment 2 was also an amendment of SAP version 01, SAP amendment 1 .

The main purpose of SAP amendment 1 was to align with all the changes made in Protocol amendments 1 and 2.

Major changes of SAP amendment 1 included:

- Updates in the sample size from 39 to 45 subjects.
- The definition of analysis sets were updated to consider subjects that have been treated with the full assigned dose as a result of co-administration with strong CYP3A4 or dual (clarified at SAP amendment 2) CYP3A4/CYP2C9 inhibitors,

- [REDACTED]

Finally a few more changes in SAP amendment 1 were made for clarification purposes and/or for consistency purposes across GvHD indications:

- The analyses sets were clarified to include only patients who signed informed consent (standard approach).
- The presentation of prior and concomitant medications were updated to follow project requirements
- The key secondary objective was clarified as per project requirements
- Presentation of graft failure assessment was clarified as part of other safety analysis.
- Sensitivity analysis was added to primary objective in order to exclude patients with protocol deviations on aGvHD assessments due to not strictly following the standard criteria
- The notable vital signs were updated to follow the latest version of WHO growth criteria
- The presentation of prior and concomitant criteria were updated to follow project requirements
- [REDACTED] as well as some PK analysis were clarified that will be explored using a separate SAP and separate CSR report.

The main purpose of the SAP amendment 2 was to remove patients classifications based on PD criteria since these were not applicable in the study. All patients who signed written informed consent were included in analyses sets. Therefore, Table 2-3 in Analysis sets section has been deleted from the SAP. Another change made in SAP amendment 2 was to move graft failure analysis from safety to efficacy analysis section.

All decisions regarding final analysis, as defined in the SAP document, have been made prior to final database lock of the study data.

2 Study design

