Should the exposure in Group 2, 3 or 4 not be confirmed following the PK sampling in at least 5 patients, additional patients will be enrolled in that specific age group until the dose/exposure is confirmed (i.e., selection of the RP2D for those ages based on exposure and safety review by the DMC). Once the RP2D is selected for Groups 2 and 3 any further eligible patients between the ages of 2 years and 12 years will be enrolled into the Phase II, and Group 4 will begin enrolling patients in the Phase I.

Although several studies of treatments for aGvHD and SR-aGvHD have included pediatric patients, it is difficult to find recent estimates for steroid response in de novo aGvHD pediatric

patients or BAT response in SR-aGvHD pediatric patients. A review of 443 patients (including 175 patients < 20 years, reported a CR/PR rate of 55% at Day 28, no association with ORR rate and patient age was found ([MacMillan et al 2010](#)). Other papers report response rates in the ranges 50-60% for de novo and SR-aGvHD ([Martin et al 2012](#)).

The sample size for the Phase II objective of measuring ORR at D28 is 45 patients regardless of age. Of these, there must be at least 20% of the patients with treatment naïve aGvHD and 40% of the patients with SR-aGvHD to ensure the sample is representative of the study population. The remaining can be filled with either diagnosis. Any patient receiving the confirmed RP2D during the Phase I will be counted towards the 45 patients.

The sample size calculation for the Ph II activity objective is based on the ORR at Day 28. Assuming the true ORR at Day 28 of the study population is 80%, an overall sample size of 45 patients would have 90% probability to have a 90% CI for ORR with lower limit $\geq 60\%$. In addition, considering the Saw-Toothed behavior of power waving for single binomial proportion using an exact method ([Chernick and Liu 2002](#)). A minimum sample size of 45 subjects would provide >85% of the probability to have a 90% CI with lower limit $\geq 60\%$. [Table 12-2](#) provides estimates of power, minimum number of responders required to have a 90% CI with lower limit of $\geq 60\%$ and two-sided 90% Clopper-Pearson CIs for various sample size. Patients treated at the RP2D from the Phase I contribute to this analysis.

Table 4-1 Probability to have a 90% CI with lower limit $\geq 60\%$ and 90% confidence intervals for different number of patients

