Sample size	Minimum No. of responders	Response Rate	Probability to have a 90% CI with lower limit $\geq 60\%$	90% CI	
37	28	0.76	0.809	0.614	0.867
38	29	0.76	0.784	0.623	0.871
39	29	0.74	0.859	0.604	0.854
40	30	0.75	0.839	0.613	0.858
41	31	0.76	0.818	0.621	0.861
42	31	0.74	0.882	0.604	0.846
43	32	0.74	0.864	0.612	0.849
44	33	0.75	0.846	0.620	0.853
45	33	0.73	0.901	0.604	0.838
46	34	0.74	0.886	0.612	0.842
47	35	0.74	0.869	0.619	0.846
48	35	0.73	0.916	0.604	0.832
49	36	0.73	0.903	0.612	0.835
50	37	0.74	0.889	0.619	0.838

5 Change to protocol specified analyses

No change from protocol

6 Appendix

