6.4 Statistical models

6.4.1 Primary analysis

Confidence interval for ORR

Responses will be summarized in terms of percentage rates with two-sided 90% confidence interval using exact binomial confidence interval (implemented using SAS procedure FREQ with EXACT statement [\[Clopper and Pearson 1934\]](#)).

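### The one planned check on mis-assessed Day 28 responses deletes the affected patients instead of correcting them, so it understates the effect of over-called responses.

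*SAP*

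**What the plan says.** SAP 3.5.4 describes the check as "A sensitivity analysis excluding subjects who had protocol deviations of organ staging or aGvHD response assessments not strictly following standard criteria", identified by two deviation codes: "PDID: OTHER03, OTHER04 per ECS) at Day 28 will be conducted". The introduction to the SAP gives the same purpose: "Sensitivity analysis was added to primary objective in order to exclude patients with protocol deviations on aGvHD assessments". Neither place mentions rescoring.

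The surrounding rules are:

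- **Assessor.** SAP 3.5.1 makes the primary endpoint investigator-reported and bases every analysis on the investigator's grade. Protocol 6.4 leaves assessors unblinded.
- **Sponsor calculation.** Protocol 12.4.1 has the sponsor calculate grade and response for data review and also for sensitivity analysis. SAP 3.5.1 retains the calculation for data review only. SAP Section 5 declares no departure from the protocol.
- **Missing data.** SAP 3.5.3: "Patients with missing assessments that prevent the evaluation of the ORR will be considered non-responders".
- **Interval.** SAP 6.4.1: "Responses will be summarized in terms of percentage rates with two-sided 90% confidence interval using exact binomial confidence interval". SAP 3.5.4 does not name an interval for the sensitivity analysis.
- **Planning benchmark.** SAP Section 4: "Assuming the true ORR at Day 28 of the study population is 80%, an overall sample size of 45 patients would have 90% probability" of a 90% interval with a lower limit of at least 60%.

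**The concern.** A sensitivity analysis for assessment error should ask what the ORR would be if the doubtful calls were put right. An over-called responder who is put right becomes a non-responder in an unchanged denominator. Deletion answers a different question, namely the ORR among patients whose assessments were not flagged.

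The visible parts of the SAP contain no other analysis aimed at mis-assessment. If responses were over-called, a reader would see only a small drop, or possibly a rise, and could take the primary result to be robust. The protocol had already named the tool for a better check, and the SAP dropped it without recording the change.

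**Working it through.** **Inputs.** N = 45, the enrolled number in the Protocol Amendment 3 rationale, taken here as the size of the Efficacy Evaluable Set (EES). The interval is two-sided 90% Clopper-Pearson (SAP 6.4.1), assumed to apply to the sensitivity analysis too. R (recorded responders), k (flagged responders who were over-called) and j (flagged patients recorded as non-responders) are assumptions, because the documents give no counts.

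**Formula.** For x responders of n, the lower limit is the 5th percentile of Beta(x, n − x + 1).

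**The plan's own figure.** At n = 45, the smallest x with a lower limit of at least 60% is 33. P(X ≥ 33) for Binomial(45, 0.80) is 0.9005, and the interval for 33/45 is 0.604 to 0.838. This matches the SAP table row "45 33 0.73 0.901 0.604 0.838". All 14 rows of that table reproduce.

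**Direction.** If the j flagged non-responders were correctly called, then:

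- Primary: R/N, lower limit from Beta(R, N − R + 1).
- Deletion: (R − k)/(N − k − j), lower limit from Beta(R − k, N − R − j + 1).
- Rescoring: (R − k)/N, lower limit from Beta(R − k, N − R + k + 1).

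Deletion and rescoring share the first parameter, and rescoring has the larger second one. Its limit is therefore lower whenever k + j > 0 (with k = 0, rescoring simply returns the primary result). With j = 0, deletion keeps the primary's second parameter and reduces the first, so its limit must fall below the primary one. A rise needs j > 0.

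**Size.** Exact 90% lower limits:

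| R | k | j | Primary | Deletion | Rescoring |
|---|---|---|---|---|---|
| 36 | 1 | 0 | 36/45: 67.7% | 35/44: 67.0% | 35/45: 65.2% |
| 36 | 3 | 0 | 36/45: 67.7% | 33/42: 65.6% | 33/45: 60.4% |
| 36 | 4 | 0 | 36/45: 67.7% | 32/41: 64.8% | 32/45: 58.0% |
| 36 | 5 | 0 | 36/45: 67.7% | 31/40: 64.0% | 31/45: 55.7% |
| 36 | 3 | 1 | 36/45: 67.7% | 33/41: 67.5% | 33/45: 60.4% |
| 36 | 3 | 2 | 36/45: 67.7% | 33/40: 69.6% | 33/45: 60.4% |
| 36 | 0 | 1 | 36/45: 67.7% | 36/44: 69.6% | 36/45: 67.7% |
| 34 | 2 | 0 | 34/45: 62.8% | 32/43: 61.2% | 32/45: 58.0% |
| 33 | 1 | 0 | 33/45: 60.4% | 32/44: 59.6% | 32/45: 58.0% |

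With five over-calls, deletion costs 67.7 − 64.0 = 3.7 points and rescoring costs 67.7 − 55.7 = 12.0 points. The point estimates are 80.0% (primary), 77.5% (deletion) and 68.9% (rescoring). With R = 34, two over-calls are enough to put the two methods on opposite sides of 60%.

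**The case against.** Several points on the other side stand:

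- A reader might infer that over-calling by itself makes the deletion analysis look better than the primary one. It does not. Deleting only over-called responders always lowers the limit. A rise needs recorded non-responders among the deleted patients.
- A reader might also infer that deletion breaches the missing-data rule. It does not. That rule covers assessments that are missing and prevent evaluation, whereas a non-standard assessment is still an assessment. The primary analysis keeps every EES patient.
- The two codes are defined in a specification outside these documents. Flagged calls could be over-calls, under-calls, or confusions between complete and partial response that leave the ORR unchanged. The direction and size of any error in this trial are therefore unknown.
- Where the organ staging itself was non-standard, recalculating from the recorded stages repeats the error. Recalculation alone is not a full remedy.
- SAP 3.3.1 tabulates deviations by category and lists them all, so flagged patients are not hidden. SAP 3.14 states that no efficacy hypothesis is tested, so crossing 60% decides nothing.

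These points limit the claim and shape the remedy. They do not make deletion an adequate check: whenever over-calls are present, it gives a more favourable limit than correcting them would. Nor do they explain why the SAP drops the protocol's sponsor-calculated sensitivity analysis without recording the change.

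**Conclusion.** The concern holds in a limited form. The deletion analysis understates the effect of over-called responses, and it can move the ORR and its lower limit upward when flagged non-responders are removed as well. In the illustrations with 36 recorded responders, the gap between deletion and rescoring is 64.0 − 55.7 = 8.3 points for five over-calls, and 69.6 − 60.4 = 9.2 points for three over-calls plus two flagged non-responders.

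These sizes rest on assumed counts, an EES of 45, the exact 90% interval, and flagged non-responders having been correctly called. An under-called patient would move the rescored result upward.

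The mismatch between protocol 12.4.1 and SAP 3.5.1, set against SAP Section 5, needs no assumed counts. The primary analysis and the sample-size figures are unaffected. The consequence is for the interpretation of robustness, so the change should be made but is not critical.

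**What to change.** Add to SAP 3.5.4, or substitute for the deletion analysis, an ORR sensitivity analysis on the full EES with the exact two-sided 90% interval:

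1. For patients flagged for a response-assessment deviation, use the sponsor-calculated Day 28 response under protocol Table 8-3, whether it moves the patient up or down.
2. Count a patient as a non-responder where the response cannot be derived, or where the organ staging itself deviated and cannot be corrected.
3. Report the number of flagged patients by deviation type and by recorded response, so that a reader can see what deletion would remove.
4. Restore the sensitivity-analysis use of sponsor-calculated response in SAP 3.5.1 and qualify its statement that all analyses use the investigator's grade. Align 3.5.4 and Section 5 with protocol 12.4.1, or record the departure in Section 5.

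The cost is a few sentences and a little programming, since the sponsor calculation is already planned for data review. The sensitivity estimate may be less favourable, and the non-responder fallback is deliberately conservative.

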3.6 Analysis of the key secondary objective

3.6.1 Key secondary endpoint

The key secondary objective of the study is durable ORR at Day 56.

Durable ORR at Day 56 is defined as the proportions of all patients who achieve a complete response (CR) or partial response (PR) at Day 28 and maintain a CR or PR at Day 56. If a patient is a CR at Day 28 and a PR at Day 56, he/she will be considered as a durable responder. A patient will not be considered a durable responder at Day 56 if any of the following events occurs:

- Not responder at Day 28
- Missing aGvHD assessment at Day 56
- No CR or PR at Day 56.
- additional systemic therapy for aGvHD prior to Day 56

Durable ORR will be calculated based on the FAS using local investigators review of aGvHD assessment data.

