If aGvHD flares occurs during the taper of immunosuppressive medications prior to Day 56, the dose of corticosteroids may be re-escalated at the Investigator's discretion and will not be considered treatment failure, as long as criteria defined in [Section 8.4.1.2](#) are not met. The taper of corticosteroids should be attempted again once the patient demonstrates a PR or CR. In these circumstances the taper of corticosteroids may extend beyond Day 56, delaying the initiation of CNI and/or ruxolitinib taper (as corticosteroid tapering must be completed prior to CNI and/or ruxolitinib taper). If aGvHD flare requires addition of a new systemic therapy due to inability to taper corticosteroids below methylprednisolone 0.5 mg/kg/day (or equivalent <0.6 mg/kg/day of prednisone) for a minimum 7 days, OR due to re-escalation of corticosteroids to

methylprednisolone >2 mg/kg/day (or equivalent >2.5 mg/kg/day of prednisone), the patient will be considered to have experienced aGvHD flare failure, and new systemic treatment is indicated per Investigator's judgement. Patients requiring new systemic treatment for aGvHD must discontinue study treatment ([Section 9.1.1](#)).

If aGvHD flare occurs after Day 56, patients may have their ruxolitinib dose increased to the prior dose level (maximum up to starting dose), their response monitored, and ruxolitinib taper attempted again if patients have a response within 28 days. If the flare is unresponsive to increased ruxolitinib dose within 28 days, or more than one flare is observed, the patient will be considered to have experienced an aGvHD flare failure, and further treatment is allowed per Investigator's judgment including: starting a new systemic treatment (refer to [Section 9.1.1](#)), or continuing ruxolitinib at the dose on which the patient was previously demonstrating a response (maximum up to starting dose) and may be continued up to Week 24.

If aGvHD flare occurs during ruxolitinib taper after Week 24 (i.e. in the case of a delayed end of ruxolitinib taper), the patient will discontinue study treatment and be treated per Investigator's judgement.

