8.3 Treatment Period

Study treatment will be initiated on Day 1 of dose assignment by IRT system.

- Day 1 is defined as the first day of treatment initiation.
- After Day1 visit will occur at the following frequency as specified in [Table 8-1](#).
 1. Every week until Week 8 (+/- 3 days)
 2. Every 4 weeks until Week 24 (+/- 7 days) or the end of treatment EOT visit
 3. Every 4 weeks until Week 48 (+/-7 days) – for patients with taper or aGvHD flare ([Section 6.1.5.1.1](#)) or the end of treatment EOT visit

Study treatment will be administered until aGvHD progression, graft failure, hematologic disease progression, occurrence of AE, or patient discontinuation [Section 9.1](#)

End of treatment visit will occur upon discontinuation of study treatment. This may be at Week 24, Week 48 (in case of taper/aGvHD flare) or earlier.

Unscheduled visits may be performed as necessary. Additional assessments may be done as per institutional guidelines at investigator's discretion at any time during the trial. aGvHD assessments performed at unscheduled visit and leading to a change in patient's management or, during treatment period to a change in patient's response should be recorded in the CRF, as well as any relevant safety assessment performed.

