12.5 Analysis of secondary endpoints

12.5.1 Efficacy and/or Pharmacodynamic endpoint(s)

The main secondary objective of the study is to estimate the proportions of all patients who achieve a complete response (CR) or partial response (PR) at Day 28 and maintain a CR or PR at Day 56. A patient will not be considered a durable responder at Day 56 if any of the following events occurs prior to or at Day 56:

- No CR or PR at Day 28 or at Day 56.
- aGvHD progression or additional systemic therapy for aGvHD

The durable response rates for ORR at Day 56 will be estimated with 90% confidence intervals on EES. Summary statistics (frequencies and percentages). The confidence intervals will be calculated based on the exact method for binomial distribution.

All secondary efficacy endpoint analyses will be analyzed using the EES.

- Overall Response Rate at Day 14, will be derived in the same way as the primary variable ORR at Day 28.
- Duration of response (DOR)

Duration of response will be calculated for patients whose overall response at Day 28 is CR or PR according to updated standard criteria ([Harris et al 2016](#)). The start date is the date of first documented response of CR or PR (i.e., the start date of response), and the end date is defined as the date of progression or the date of addition of systemic therapies for aGvHD, since this constitutes a non-response.

Death without prior observation of aGvHD progression and onset of chronic GvHD are considered to be competing risks.

Duration of response will be censored at the last response assessment prior to or at the analysis cut-off date, if no events/competing risk occurred before or at of cut-off date.

DOR will be listed and summarized for all patients on the EES with overall response of CR or PR at Day 28.

- Overall survival (OS)

Overall survival is defined as the time from date of the start of study treatment to date of death due to any cause. If a patient is not known to have died, then OS will be censored at the latest date the patient was known to be alive (on or before the cut-off date).

The OS distribution will be estimated using the Kaplan-Meier method, and the Kaplan-Meier curves, medians, 1, 2, 6, 12, 18 and 24 month survival estimates and 95% confidence intervals will be presented.

- Event Free Survival (EFS)

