3.7 Analysis of secondary efficacy objective(s)

3.7.1 Secondary endpoints

- **Overall Response Rate at Day 14**

Overall Response Rate at Day 14 is defined as the proportion of patients with complete response (CR) or partial response (PR) at Day 14 according to standard criteria [\[Harris 2016\]](#).

- **Duration of response (DOR)**

Duration of response will be calculated for patients whose overall response at Day 28 is CR or PR according to updated standard criteria [\(Harris et al 2016\)](#). The start date is the date of first documented response of CR or PR (i.e., the start date of response), which could be prior to or at Day 28. If it's prior to Day 28, there should not be progression or addition of systemic therapies for aGvHD between the start date of response and Day 28. The end date is defined as the date of progression or the date of addition of systemic therapies for aGvHD on or after Day 28, since this constitutes a non-response. The date of progression will be the earliest date of PD recorded in the aGvHD assessment CRF page or the date of death due to aGvHD in the death CRF page.

Death without prior observation of aGvHD progression (i.e. date of death due to non aGVHD reason (Other) in the death CRF page) and onset of chronic GvHD are considered to be competing risks.

Duration of response will be censored at the last response assessment prior to or at the analysis cut-off date, if no events/competing risk occurred before or at of cut-off date.

- **Best Overall Response**

Best overall response (BOR) is defined as proportion of patients who achieved overall response (CR or PR) at any time point up to and including Day 28 and before the start of additional systemic therapy for aGvHD.

An additional analysis will include BOR at any time point up to the data cut-off date and before the start of additional systemic therapy for aGvHD. A swimmer plot for overall response by age group, SR-aGvHD vs Treatment Naive and formulation will also be provided for all treated subjects.

- **Overall survival (OS)**

Overall survival is defined as the time from date of the start of study treatment to date of death due to any cause. If a patient is not known to have died, then OS will be censored at the latest date the patient was known to be alive (last contact date on or before the cut-off date).

- **Event Free Survival (EFS)**

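### The SAP's failure list for durable response at Day 56 leaves out aGvHD progression, which the protocol counts as failure, while SAP Section 5 declares no change

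*SAP*

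**What the plan says.** Protocol 12.5.1 defines durable response as CR or PR at Day 28 that is maintained at Day 56. It withholds that status "if any of the following events occurs prior to or at Day 56". Two items follow: no CR or PR at either visit, and "aGvHD progression or additional systemic therapy for aGvHD". Progression is thus a failure in its own right.

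SAP 3.6.1 repeats the definition and then writes "A patient will not be considered a durable responder at Day 56 if any of the following events occurs". Its four items are non-response at Day 28, a missing Day 56 assessment, no CR or PR at Day 56, and additional systemic therapy before Day 56. SAP 3.6.3 only points back to the missing-data rules of SAP 3.5.3, which do not mention progression. SAP Section 5, on changes to the protocol's analyses, reads in full "No change from protocol".

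For duration of response, SAP 3.7.1 ends the response at "the date of progression or the date of addition of systemic therapies for aGvHD on or after Day 28".

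Two neighbouring passages also disagree. SAP 3.6.1 bases durable ORR on the FAS, while SAP 3.6.2 and Protocol 12.5.1 use the EES. Protocol 6.5.2.1.2 makes patients who meet its non-hematologic discontinuation criteria after Day 28 non-responders for the Day 56 endpoint, but Protocol 12.4.3, Protocol 12.5.1 and SAP 3.6.1 do not carry that rule.

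**The concern.** This endpoint exists to show that the Day 28 response lasts. A list that checks only Day 28, Day 56 and new therapy does not see a response that was lost and regained in between. The reported rate would then rest on a looser definition than the protocol's, under a statement that nothing changed. The SAP could also count one patient as a durable responder and, a few tables later, record that patient's response as having ended before Day 56.

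**Working it through.** **1. The plan's own figure.** The documents give no design figure for durable ORR. The nearest is for ORR at Day 28 (Protocol Table 12-2): n = 45, at least 33 responders, true rate 80%, probability 0.901, 90% CI 0.604 to 0.838. The exact binomial tail P(X ≥ 33 | n = 45, p = 0.80) is 0.9005, and the Clopper-Pearson 90% interval for 33/45 is 0.604 to 0.838. Both reproduce, and the present point changes neither.

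**2. The two lists side by side.**

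| Event | Protocol 12.5.1 | SAP 3.6.1 |
|---|---|---|
| No CR/PR at Day 28 | failure | failure |
| No CR/PR at Day 56 | failure | failure |
| Day 56 assessment missing | failure (Protocol 12.4.3) | failure |
| New systemic therapy before Day 56 | failure | failure |
| New systemic therapy starting on Day 56 | failure | not listed |
| Progression by Day 56, no new therapy, CR/PR at Day 56 | failure | not listed |

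**3. Direction.** Every SAP failure is also a protocol failure, and the last two rows are failures only under the protocol. On the same analysis set, the SAP rate is therefore never below the protocol rate.

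**4. Who is affected.**
- Response and progression are scored against the organ stage at screening and Day 1 (Protocol Table 8-3). Progression means at least one organ worse by at least one stage, with no involved organ improved.
- The patient must respond at Day 28, then lose every improvement and become worse than baseline in some organ, then regain CR or PR by Day 56.
- No new systemic therapy may have been given. SAP 6.4.3 does not count steroid changes as new therapy. Under Protocol 6.1.5.1.1, re-escalating steroids for a flare before Day 56 is at the investigator's "discretion and will not be considered treatment failure, as long as criteria defined in" Section 8.4.1.2 are not met.
- Assessments are weekly to Day 56 (Protocol 8.4.1.2), so progression at Week 6 with PR at Week 8 would be seen and recorded.
- Nothing in the CR and PR definitions (SAP 3.5.1) excludes this patient. They bar additional therapy given for an earlier progression, not the progression itself.

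The result is failure under Protocol 12.5.1, durable under SAP 3.6.1, and response ended at Week 6 under SAP 3.7.1.

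**5. Size.** With k affected patients among 45, SAP rate minus protocol rate = k/45. For k = 1 this is 2.2 points, for k = 2 it is 4.4, and for k = 4 it is 8.9. To set that against the precision, take an arbitrary SAP count of 27 (an assumption, not a figure from the documents), with exact 90% intervals:
- k = 0: 27/45 = 60.0% (46.7 to 72.3)
- k = 1: 26/45 = 57.8% (44.5 to 70.3)
- k = 2: 25/45 = 55.6% (42.3 to 68.3)

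The shift from one or two patients is small against an interval about 26 points wide (72.3 − 46.7 = 25.6).

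**The case against.** The best defence is that the SAP keeps the protocol's headline definition, which requires the response to be maintained, and that a patient who became worse than baseline did not maintain it. This has some force, because the objectives tables in both documents also omit progression. But the SAP gives no rule for applying that requirement, and a programmer would code the explicit list.

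The path is also narrow, and that stands. An ordinary flare that gives back part of the Day 28 gain is not progression and, by itself, is a failure under neither document. The Day 56 therapy boundary is narrower still: SAP 3.5.1 already classes patients who need additional systemic therapy as non-responders, which may catch most such cases.

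A reader might infer more than the documents support:
- **That a criterion was removed.** The SAP introduction says of amendment 1, "The key secondary objective was clarified as per project requirements". No earlier SAP text is available, so this does not show that progression was ever listed and then taken out.
- **That responses regained after ruxolitinib stopped would count as durable.** Protocol 8.3 says "Study treatment will be administered until aGvHD progression". However, the mandatory discontinuations in Protocol 9.1.1 do not include progression after Day 28. Where treatment does stop for progression, new therapy is plausible, and the SAP list already covers it.
- **That the number affected can be estimated.** The adult and adolescent trial summarised in Protocol 1.1.2.1.2 studied a different population, and its durable-response definition cannot be checked here.

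**Conclusion.** The mismatch is real and undeclared. SAP 3.6.1 omits a failure event that Protocol 12.5.1 names, and its therapy window stops short of Day 56. The effect can only raise the durable rate, by 2.2 points per affected patient. That size assumes 45 patients and the same analysis set under both definitions. How many patients are affected cannot be known from the documents, and it may be none. One secondary estimate is touched, while the primary endpoint and the sample-size figures are not. Severity is minor.

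The protocol wording has a flaw of its own. Read literally, its window also fails a patient who progressed before a genuine Day 28 response, so copying it unchanged would not be ideal.

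The FAS/EES conflict is probably only wording. The planned intensities in SAP 3.4.1 (20 mg, 10 mg and 8 mg/m² per day) are twice the starting doses of 10 mg, 5 mg and 4 mg/m² BID. This suggests that the starting doses became the RP2D and that the two sets coincide, but that is an inference.

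**What to change.** In SAP 3.6.1:
- Add a failure event: aGvHD progression recorded after the Day 28 response, up to and including Day 56, taken from the progression record already derived for duration of response.
- Extend the therapy item to include Day 56 itself.
- Replace FAS by EES.

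In SAP Section 5, state that progression before a Day 28 response is not counted as failure, because the literal protocol text would count it. If the looser definition is intended, declare that in Section 5 and report the protocol definition beside it.

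Separately, Protocol 6.5.2.1.2 must be reconciled with Protocol 12.4.3, Protocol 12.5.1 and SAP 3.6.1, so that one stated endpoint rule covers the discontinuations it describes after Day 28.

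The SAP part costs a few lines of text and code, and the reported durable ORR may be slightly lower. Any change to protocol text needs a written amendment with the approvals in Protocol 14.1, so the SAP correction or declaration is the practical route.
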